### **INTEREVNTIONAL GROUP:**

Patients in Interventional group in first set will perform 3 minute of cycling ,1 set of hand grippers 1.5 to 2.5 lbs (10 to 12 reps) and 1 set of biceps resistive exercises 1 Kg to 3 kg (10 to 12 reps) followed by 3minute of pause. In second set patient will perform 3 minutes of stationary cycling , 1 set of quadriceps resistive exercises 1 to 3 Kg (10 to 12 reps) again followed by 3 minutes of pause and in third set patient will perform 3 minutes of treadmill walk at 1.5 to 4 speed, and 1 set of standing ankle pumps (10 to 12 reps).

Patients in both groups will perform cool down exercises that include again breathing exercises, stretching and active exercises. Post exercise vitals will be recorded in both groups.

Figure 3: Patient performing treadmill as a part of treatment protocol

## DATA ANALYSIS PROCEDURE:

All the patients were assessed at the baseline before the intervention and at the completion of the study. Data was analyzed by using IBM SPSS 21 (Statistical Package for Social Sciences) and expressed in the form of tables and graphs.

## CURVES OF NORMALITY

[figure not shown]

Figure 4: Normality test (histograms) for Baseline Vitals, A: Heart rate, B: Respiratory rate, C: Saturation, D: Systolic BP, E: Diastolic BP

We applied normality test on Baseline vitals. Histogram showed abnormally skewed curves for Heart rate, respiratory rate and oxygen saturation ( $p=0.000, 0.030, 0.004$ ) respectively and normally skewed curves for systolic and diastolic BP ( $p=0.396$  and  $0.108$ ) respectively. Test of choice is non-parametric, Mann-Whitney U test for the comparison between groups (sample size  $< 30$  in each group).

[figure not shown]

Figure 5: Normality test (histograms), A: Ejection Fraction

We applied normality test on baseline ejection fraction. Histogram showed abnormally skewed curve for ejection fraction ( $p=0.001$ ). Test of choice is non-parametric, Mann-Whitney U test for the comparison between groups (sample size  $< 30$  in each group.)

[figure not shown]

Figure 6: Normality test (histograms), A: Cholesterol, B: Triglycerides

We applied normality test on baseline cholesterol and triglycerides. Histogram showed abnormally skewed curves for cholesterol and triglycerides ( $p=0.000, 0.026$  respectively). Test of choice is non-parametric, Mann-Whitney U test for the comparison between groups (sample size  $< 30$  in each group)

[figure not shown]

Figure 7: Normality test (histograms) for Baseline Quality of life, A: Emotional state, B: Physical state, C: Social state

We applied normality test on baseline quality of life including its three domains of emotional, physical and social state. Histogram showed abnormally skewed curve for emotional ( $p=0.025$ ) and normally skewed curves for physical and social state ( $p=0.129$  and  $0.577$  respectively). Test of choice is non-parametric, Mann-Whitney U test for the comparison between groups (sample size  $< 30$  in each group.)

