**DESIGN: Randomized Control Trail**

**DATA COLLECTION PROCEDURE:**

After screening of more than 50 MI patients 26 stable post MI patients both males and females on the basis of inclusion and exclusion criteria were enrolled. After enrollment final step for inclusion in study was 6 minute walk test. All patients performed treadmill 6 minute walk test. Patients that successfully completed initial 3 min of walk test were included in the study. Informed consent was signed by all patients as an agreement to participate in research. Total patients at end of study was 26 with drop outs of 4 .After enrollment in study 1st day was pre assessment day.1st step was selection in either control or experimental group. Lottery method was used for random allocation of patients. Self structured questionnaire was filled that included demographics, patient past medical, surgical, drug history, comorbidites, risk stratification. Basic baseline evaluation was done that included ECG, urea, creatinine, lipid profile. Pre echocardiography of all patients was done Pre MAC New QLMI was filled by examiner herself. After completion of all pre assessment exercise session of the patient was started from next session. Total weeks of treatment session were 6. Exercise was performed 3 times a week on alternating days. Total days of exercise were 18. Before treatment session proper warm up for 15 minutes was done Pre vitals including heart rate, BP, Respiratory rate, SpO2 was recorded. Karvonens formula was used to calculate 60-80% of target heart rate in all patients .The goal of exercise was to reach target heart rate. Emergency trolley consisting of major life saving drugs was available that included (Angisid, Injection Atropine, Adrenaline, Heparin, Lignocaine, Streptokinase, Nitroglycin, Normal Saline, Glucose) plus examiner was qualified in ACLS. Patient speed was increased gradually from first to six weeks depending on each patient target heart rate. Likewise weight in quadriceps resistive exercise and hand grippers were increased gradually with number of repetitions remaining same. Rating of perceived exertion and fatigue scale was used to mark patient dyspnea and fatigue level. Patients in control group were given standard aerobic interval treatment while patient in experimental group was given aerobic plus resistance interval treatment. During session continuous vital monitoring was done using saturation probe and cardiac monitor. After completion of session post vitals HR, BP, RR, Spo2 RPE and fatigue Cool down exercises were performed to stabilize patient. After completion of total 6 weeks of intervention patients post tests were done that included Echocardiography, lipid profile post and Mac New QLMI.

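### The plan does not say which values the Mann-Whitney test compares, and it plans no effect estimate, confidence interval or use of the baseline values already collected

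*Combined protocol and SAP*

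**What the plan says.** The Curves of Normality section is the only place in the supplied text that names a statistical test. It reports normality checks on four sets of baseline variables: vitals, ejection fraction, lipids and quality of life. For example: "We applied normality test on baseline ejection fraction". After each set comes the same conclusion: "Test of choice is non-parametric, Mann-Whitney U test for the comparison between groups", with fewer than 30 patients per group as the added reason. The conclusion does not change where the check was passed, as with the "normally skewed curves for physical and social state".

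The Data Analysis Procedure section adds only that patients were assessed before the intervention and at completion, the software, and the display format.

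The Data Collection Procedure section shows that paired measurements exist. Before treatment: "Basic baseline evaluation was done that included ECG, urea, creatinine, lipid profile", and "Pre echocardiography of all patients was done Pre MAC New QLMI was filled by examiner herself". Afterwards: "After completion of total 6 weeks of intervention patients post tests were done that included Echocardiography, lipid profile post and Mac New QLMI".

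**The concern.** A between-group test needs a stated quantity, and none is given. If the sentence describes a check of baseline comparability, no six-week comparison is named anywhere in the supplied text. If it describes the six-week comparison, the choice between final values and changes is left open, and the method has been justified by the shape of a different set of numbers, the baseline values. On either reading the product is a p-value without a size.

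With about 26 patients that matters. A non-significant p-value cannot tell a reader whether a sizeable effect on ejection fraction, lipids or quality of life has been excluded; an interval can. The baseline value of each of these outcomes is also on file and could narrow that interval, but no use of it is planned.

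**Working it through.** **1. Variables covered.** Five vitals + ejection fraction + two lipids + three MacNew domains = 11. Four are reported as normal at baseline: systolic BP (p = 0.396), diastolic BP (0.108), physical state (0.129) and social state (0.577). The other seven are reported as not normal. Mann-Whitney is named for all 11, so the check did not change the method for any of them.

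**2. Figure to reproduce.** None. The documents give no alpha, power, effect size, SD, correlation or arm sizes. They say "Lottery method was used for random allocation of patients" and "Total patients at end of study was 26 with drop outs of 4".

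**3. Assumptions for sizing, none from the documents.** 13 per arm (26/2), two-sided 0.05, SD = 1, a shift of 1.0 SD, and correlation ρ between baseline and six-week values from 0 to 0.9.

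**4. Large-sample expectation.** Relative variance is 1 for six-week values, 2(1 − ρ) for changes and 1 − ρ² for baseline adjustment. Changes beat six-week values only when 2(1 − ρ) < 1, that is ρ > 0.5. Adjustment should multiply the interval width by √(1 − ρ²): 0.98 at ρ = 0.2, 0.87 at 0.5 and 0.60 at 0.8.

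**5. Simulation.** Power comes from 8,000 trials per cell, using exact Mann-Whitney critical values (U ≤ 45, size 4.4%). Half-widths come from 3,000 to 4,000 trials per cell. Rank ANCOVA means ranks of the six-week value regressed on group and on ranks of that outcome's own baseline; its interval comes from inverting that test.

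Normal data:

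| ρ | Power %, Mann-Whitney, six-week | Power %, Mann-Whitney, change | Power %, rank ANCOVA | Half-width (SD), Mann-Whitney, six-week | Half-width (SD), rank ANCOVA |
|---|---|---|---|---|---|
| 0 | 64.6 | 36.4 | 65.0 | 0.84 | 0.83 |
| 0.2 | 64.7 | 45.0 | 66.4 | 0.84 | 0.82 |
| 0.5 | 65.1 | 65.0 | 76.1 | 0.84 | 0.73 |
| 0.7 | 64.1 | 84.8 | 87.0 | 0.84 | 0.62 |
| 0.8 | 63.7 | 96.1 | 95.5 | 0.84 | 0.54 |
| 0.9 | 64.1 | 99.9 | 99.6 | 0.84 | 0.40 |

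The width ratios agree with step 4: 0.82/0.84 = 0.98, 0.73/0.84 = 0.87, 0.54/0.84 = 0.64.

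The unstated quantity matters in both directions. Mann-Whitney on changes is 64.6 − 36.4 = 28.2 points below Mann-Whitney on six-week values at ρ = 0, and 96.1 − 63.7 = 32.4 points above it at ρ = 0.8.

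**6. Range.** Skewed (lognormal) data at 13 per arm: half-width 0.64 SD unadjusted against 0.62 / 0.55 / 0.39 SD adjusted at ρ = 0.2 / 0.5 / 0.8. With 11 per arm at ρ = 0.5: 0.91 against 0.81 SD (normal) and 0.70 against 0.62 SD (lognormal).

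**7. How much of the gain is adjustment.** The exact Mann-Whitney test is slightly conservative and the rank ANCOVA is t-based. In a separate run (normal, ρ = 0.5), Mann-Whitney had 64.6% power, the t-based rank test without the covariate 66.6%, and rank ANCOVA 75.6%. Of the 75.6 − 64.6 = 11.0 points, 66.6 − 64.6 = 2.0 are calibration and 75.6 − 66.6 = 9.0 are adjustment.

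**8. Behaviour of the adjusted method.** Type I error was 4.6 to 5.4% and interval coverage 94.4 to 95.8%. The interval excluded zero exactly when the test rejected. Because ranks move in steps, a trial difference giving a group coefficient of exactly zero existed in only 0 to 1% of simulated trials, so the point estimate needs a sign-change rule.

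**The case against.** The strongest reply is that Mann-Whitney is a sound choice for a small randomised trial with skewed data. The demonstrable gaps are then the unnamed quantity and the missing estimate, and both close by stating the quantity and reporting the Hodges-Lehmann shift with its interval. Baseline adjustment would be a refinement whose benefit rests on a correlation nobody has reported. Power figures also cannot improve data already collected, and the documents are largely written in the past tense. Promoting a new test over the only one named, after the data have been seen, would create a problem of its own.

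Most of this stands. It is why the fix keeps Mann-Whitney as the named test and treats the adjusted result as supportive if the data have been analysed. It does not remove the point: the simple fix is itself absent from the plan, and the narrower interval is available even in a re-analysis when the correlation is about 0.5 or more.

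Three stronger readings are tempting, and the documents do not support them.

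- A reader might infer that choosing the test from baseline normality makes the comparison invalid or biased. Allocation is described as random, and Mann-Whitney is a valid comparison of randomised groups on either six-week values or changes. Baseline shape is a weak reason for the choice, but a rank test is defensible at this size.
- A reader might infer that no six-week comparison was intended. The text is silent on the quantity; it does not say the test was confined to baseline.
- A reader might infer that a fixed amount of power was thrown away. That depends on an unreported correlation, and at 0.2 or below the gain over Mann-Whitney on six-week values is close to nil.

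**Conclusion.** The point holds as one of precision and interpretability, and it should be corrected. The text names an unadjusted test for 11 variables without saying what is compared, and plans no estimate, interval or use of the available baselines. The need for an estimate and interval does not depend on any assumption.

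The benefit of adjustment does. Under the normal-data assumptions above, the half-width falls by 0.84 − 0.82 = 0.02 SD at correlation 0.2, by 0.84 − 0.73 = 0.11 SD at 0.5 and by 0.84 − 0.54 = 0.30 SD at 0.8. Confidence is moderate, because arm sizes, effect size and correlation are all assumed and the conclusion rests on the text supplied.

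**What to change.** **Step 1, needed in any case.** In the Curves of Normality section, state that the between-group comparison of ejection fraction, lipids and MacNew domains uses six-week values. State also which reading is used for the vitals, which are taken both before and after exercise. If the sentence was meant as a baseline check, say so and add the six-week comparison. Keep Mann-Whitney as the named test and report with it the Hodges-Lehmann shift and its matching 95% confidence interval.

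**Step 2, baseline-adjusted analysis.** For each six-week outcome with a baseline value, add a rank ANCOVA: ranks of the six-week value on group plus ranks of its own baseline. For the interval, subtract a trial difference from the experimental arm's six-week values, re-rank and refit; the differences not rejected at 0.05 form the 95% interval. Take as the estimate the difference at which the group coefficient changes sign, or the midpoint if it changes over a range. Do not pair this test with an ordinary ANCOVA interval. In lognormal simulations (13 per arm, shift 0.5 to 1.0 SD, correlation 0.2 to 0.8) the test rejected while that interval covered zero in 4 to 18% of trials.

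**Status.** If the data have not been analysed, the adjusted analysis may be pre-specified as the main one. If they have, label it post hoc and supportive.

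**Cost.** One degree of freedom per model, revised wording and a short program run on data already held. The intervals assume that the effect is a shift. Almost nothing is gained at correlation 0.2 or below. At about 0.9 with normal data and a 0.5 SD effect, rank ANCOVA has less power than Mann-Whitney on changes: 67 against 74% at 13 per arm and 56 against 66% at 11 per arm.

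### Plain Mann-Whitney is named for six variables that match the 6-week post tests, with no time point, primary outcome or multiplicity rule in the available text and the baseline values left unused

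*Combined protocol and SAP*

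**What the plan says.** The design is a randomized two-arm comparison. Data Collection Procedure describes baseline echocardiography, lipid profile and MacNew questionnaire, and then the follow-up: "After completion of total 6 weeks of intervention patients post tests were done that included Echocardiography, lipid profile post and Mac New QLMI". On numbers it reports "Total patients at end of study was 26 with drop outs of 4"; arm sizes are not given.

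Data Analysis Procedure gives the software and the assessment times, and little else: "All the patients were assessed at the baseline before the intervention and at the completion of the study".

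The choice of test appears only in Curves of Normality, after each block of normality checks:

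- Ejection fraction: "We applied normality test on baseline ejection fraction".
- Lipids: "We applied normality test on baseline cholesterol and triglycerides".
- Quality of life: "We applied normality test on baseline quality of life including its three domains of emotional, physical and social state".

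Each block ends with the same conclusion: "Test of choice is non-parametric, Mann-Whitney U test for the comparison between groups". A further block applies the same conclusion to five baseline vital signs.

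None of these sections states a primary outcome, a significance level, a hierarchy of outcomes or a multiplicity adjustment. The opening part of the document was not available for review.

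**The concern.** Three things are left open together.

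1. **Which values are compared.** The test is chosen from baseline distributions, and the sentence does not say whether it will be applied to baseline values, 6-week values or both.
2. **Which result answers the trial's question.** If the six variables are the 6-week outcomes, each gets the same test and none is marked as decisive. A single p-value just below 0.05 among six is then weak evidence of a treatment effect, yet nothing in the available text stops it being reported as the trial's finding.
3. **Whether baseline is used.** A plain two-sample rank test on 6-week values makes no use of each patient's own baseline measurement. In a trial of 26 patients that gives up precision that costs no extra data.

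**Working it through.** **Plan's own figure.** There is none to reproduce: no significance level, power or overall error rate is stated.

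**Inputs from the documents.** The 6-week list in Data Collection Procedure is matched to the blocks in Curves of Normality:

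| 6-week post test | Variables given the Mann-Whitney test | Count |
|---|---|---|
| Echocardiography | ejection fraction | 1 |
| Lipid profile | cholesterol, triglycerides | 2 |
| MacNew | emotional, physical, social | 3 |
| Total | | 6 |

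**Assumptions.** Each test is two-sided at 5%, all six are tested at 6 weeks, and the arms do not differ on any of them. Correlations between outcomes are not in the documents, so a range is shown. Arm sizes are taken as 13/13 (26 split equally) or 11/11 (22 split equally, if the four drop-outs came out of the 26).

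**Step 1, independent outcomes.** P(at least one false positive) = 1 − 0.95^6 = 1 − 0.7351 = 0.265.

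**Step 2, one common correlation across all six** (simulated normal test statistics, 1,000,000 draws):

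| Common correlation | 0 | 0.3 | 0.5 | 0.7 | 0.9 |
|---|---|---|---|---|---|
| At least one of six | 26.5% | 24.1% | 20.7% | 16.4% | 10.8% |

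**Step 3, correlation high only within families:**

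| Lipids | MacNew domains | Between families | At least one of six |
|---|---|---|---|
| 0.3 | 0.5 | 0 | 24.8% |
| 0.5 | 0.7 | 0 | 23.0% |
| 0.5 | 0.8 | 0.1 | 22.0% |
| 0.7 | 0.8 | 0.2 | 21.0% |

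**Step 4, exact Mann-Whitney in place of the nominal 5%** (no ties). The true size per test is 0.0441 at 13/13 and 0.0473 at 11/11. For independent outcomes, 1 − (1 − 0.0441)^6 = 0.237 and 1 − (1 − 0.0473)^6 = 0.252. By simulation (100,000 draws):

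| Common correlation | 0 | 0.3 | 0.5 | 0.7 |
|---|---|---|---|---|
| 13/13 | 23.7% | 22.1% | 19.3% | 15.6% |
| 11/11 | 25.2% | 23.5% | 20.5% | 16.6% |

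These are close to the nominal figures. Most are slightly lower, but the 11/11 value at correlation 0.7 is marginally higher (16.6% against 16.4%).

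**Step 5, what the remedies do.** Holm over six compares the smallest p-value with 0.05/6 = 0.0083. At correlations 0, 0.3, 0.5 and 0.7 it gives an overall rate of 4.9%, 4.6%, 4.1% and 3.4%. One primary at 5% that gates Holm on the other five gives 5.0% throughout.

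**Step 6, power.** The assumed case is a true difference of 1.0 SD in one outcome only, with correlation 0.3 between outcomes:

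| Analysis of that outcome | Unadjusted 5% | Holm over six |
|---|---|---|
| Mann-Whitney, 13/13 | 64% | 35% |
| Mann-Whitney, 11/11 | 58% | 30% |
| Rank ANCOVA, 13/13, baseline to 6-week correlation 0.5 | 76% | 49% |
| Rank ANCOVA, 13/13, baseline to 6-week correlation 0.7 | 88% | 66% |

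**The case against.** **The test sentence may concern baseline comparability only.** It follows baseline normality checks each time, and it is also attached to vital signs, which the 6-week list does not name. This stands as a limit: a reader might infer that the plan commits to six tests at 6 weeks, and the documents do not say so. It does not clear the plan, because on that reading the available text names no test for the 6-week outcomes.

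**A primary outcome may be recorded elsewhere.** This also stands. Part of the document was not available, so one cannot conclude that the trial had no primary outcome, only that the available text does not show one.

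**The percentages rest on assumed correlations.** Correct. A reader might take 16% as a lower limit, but a common correlation of 0.9 gives about 11%. That would require ejection fraction, lipids and quality of life to move almost as one; structures with correlation only within families give 21-25%.

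**Counting all eleven variables would make matters worse.** A reader might add the five vitals and arrive at 1 − 0.95^11 = 43% for independent tests. The documents do not support this, since the vitals are not named among the 6-week post tests.

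**Mann-Whitney is a valid randomized comparison.** Also correct. Leaving baseline unused is a loss of precision, not a bias, and it is separate from multiplicity. Swapping the named test for another after seeing results would add the very flexibility at issue, so the remedy has to label such an analysis.

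**Conclusion.** The concern holds in a conditional form. The plan names one unadjusted rank test for six variables that correspond to the 6-week outcomes, without saying when it is applied. The available text does not identify which result is confirmatory. If all six are tested at 6 weeks at two-sided 5%, the chance of at least one false positive with no true difference is most plausibly between a fifth and a quarter. It is lower only if all six outcomes are strongly correlated with each other. These figures are illustrations: the time point, the 5% level, the correlations and the arm sizes are all assumptions. The unused baseline values are a second, smaller weakness with a ready remedy.

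This should be corrected because it bears on how every efficacy result is read. Confidence is medium, since the 6-week reading is inferred and part of the document is unseen.

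**What to change.** 1. **Time point.** State that the between-group tests use 6-week values.
2. **Baseline.** Add a baseline-adjusted comparison, for example rank ANCOVA, for each of the six. Make it the main analysis only if outcome data are still unseen. Otherwise label it post hoc and show it beside Mann-Whitney, whether or not an earlier record fixes a primary outcome.
3. **If an earlier record names a primary, or data are unseen and one is named now.** Test it at two-sided 5%, and test the other five with Holm only if it is significant.
4. **Otherwise.** State that no primary was pre-specified, label the results exploratory, and report all six comparisons with Holm-adjusted p-values beside the unadjusted ones.

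**Cost.** One paragraph if outcome data are unseen. If they have been analysed, as the past tense in Data Collection Procedure and Data Analysis Procedure suggests, six comparisons must be re-reported and the conclusions relabelled. Fewer results will be nominally significant, and a failed primary allows no formal claim on the other five. Holm also costs power, roughly halving it in the illustration above; baseline adjustment recovers part of that loss.
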